8 PHARMACEUTICAL INFORMATION

A list of the adverse events and potential risks associated with the investigational agent administered in this study can be found in Section [10.1](#).

8.1 CTEP AGENT BIRINAPANT ([NSC 756502](#))

Chemical Name: Propanamide, N,N'-[$(6,6'$ -difluoro[2,2'-bi-1H-indole]-3,3'-diyl)bis[methylene[(2R,4S)-4- hydroxy-2,1-pyrrololidinediyl][(1S)-1- ethyl-2-oxo-2,1-ethanediyl]]]bis[2-(methylamino)-, (2S,2'S)-]

Classification: SMAC mimetic selective IAP antagonist

Other names: TL32711

Molecular Formula: C42H56F2N8O6 **Molecular Weight:** 806.9 g/mol as free base

Approximate Solubility: Solubility in 50mM citrate buffer pH 5 is \geq 5 mg/mL

Mode of Action: Birinapant is a potent and selective small molecule peptidomimetic of SMAC that binds to multiple members of the IAP family. SMAC (secondary mitochondrial activator of caspase) is a natural IAP antagonist that rapidly antagonizes IAPs resulting in caspase activation and apoptosis. Members of the Inhibitors of Apoptotic Proteins (IAPs) family can block cell death by directly binding to and suppressing caspase activity. The activity of the IAPs is regulated by SMAC.

How Supplied: IGM Biosciences supplies and CTEP, DCTD, NCI distributes birinapant in single-use 10 mL amber-glass vials containing sterile-filtered liquid in 50 mM citrate buffer solution pH 5. Each vial contains 10 mg (1 mg/mL, 10 mL) of birinapant as a clear, colorless to pale yellow drug solution. Excipients include citric acid monohydrate, sodium citrate dihydrate, sodium chloride, citric acid and sodium citrate.

Each vial is packaged in a secondary carton to further protect the product from potential photodegradation on exposure to UV/visible light.

Preparation: Thaw birinapant at ambient temperature for approximately 2.5 hours (or at 2-8 °C for 16-64 hours) while protected from light. Invert the vials several times to mix.

Aseptically remove desired dose from the vial and inject into an intravenous bag containing sterile 250 mL 0.9% sodium chloride injection USP. Invert several times to mix. Inspect bag for particulates. If particulates are present, do not use and repeat the preparation process using new vials. If particulates are present for a second time, report the finding to PMB. Do not use a filter.

If preparing a large dose, remove a sufficient amount of normal saline from the IV bag beforehand to accommodate the birinapant volume. There is no specific final concentration range

required by the manufacturer.

The manufacturer conducted compatibility studies with latex-free materials only. Only latex-free infusion bags, administration sets and syringes may be used to prepare birinapant doses.

Vials are for single use only and must be discarded after preparation.

Storage: Store birinapant in the freezer (-10 to -30° C) in the carton that is provided by the manufacturer. The agent is potentially light sensitive.

If a storage temperature excursion is identified, promptly return birinapant to between -10 to -30°C and quarantine the supplies. Provide a detailed report of the excursion (including documentation of temperature monitoring and duration of the excursion) to

[contact] for determination of suitability.

Stability: Shelf life studies of intact vials are ongoing. The prepared solution is stable for up to 4 hours at -room temperature in ambient light. The dose must be administered within 4 hours after preparation. Only store prepared solution at room temperature.

Route and Method of Administration: Intravenous over 30 minutes. Solution must be diluted prior to administration and should not be filtered at any point.

Potential Drug Interactions: The drug-drug interaction potential of birinapant has not been fully assessed. In vitro studies indicate that birinapant is not a substrate for CYP450-mediated metabolism. Birinapant is not an inhibitor of CYP 1A2, 2A6, 2B6, 2C8, 2C9, 2C19, 2D6, 2E1 and 4A11, but some moderate, partially-reversible, time-dependent inhibition of CYP3A4/5 is observed. Overall results indicate that birinapant has a low potential for CYP-mediated drug interactions.

Birinapant is not a P-gp substrate; however, P-gp inhibition was observed at 3 μ M in vitro. For reference, the average Cmax observed was approximately 5 μ M following a dose of 47 mg/m2. Birinapant is likely a substrate of the OATP1B3 transporter, which may be involved in the biliary excretion of birinapant. Birinapant moderately binds to plasma proteins. The excretion of the drug is mainly biliary per PK studies in animals. In humans, a phase I trial (12), has shown that the renal excretion of the drug is low.

Population PK analysis showed that the central volume of distribution increased with body surface area (BSA) and a reduction in the central volume of distribution of approximately 60% was observed when birinapant was administered in combination with carboplatin/paclitaxel relative to birinapant alone and other combination therapies studied. Also, a reduction in clearance of birinapant of 65% was observed with the combination of birinapant and carboplatin/paclitaxel.

At present, based on the available clinical data, it is judged that no change of birinapant dosing is indicated for the combination with carboplatin/paclitaxel, however awareness of the above PK observations in patient studies using this combination is important.

Patient Care Implications: The pharmaceutical collaborator reports that birinapant synergizes with TNF α in vitro. Patients with a serious active infection (within 2 weeks of dosing) or who have ongoing autoimmune disease or a recent history (within last 5 years) of autoimmune disease should not receive birinapant. Patients receiving anti-TNF therapies should not receive birinapant.

Birinapant should not be administered to women study participants who are pregnant or nursing. Women and men of child-bearing potential must agree to use adequate contraception (hormonal or barrier method of birth control; abstinence) prior to study entry and for the duration of study participation. The effect of birinapant on male fertility is unknown; however, a 14 week animal study indicated that it caused testicular atrophy/degeneration with effects on spermatogenesis noted microscopically and reduced sperm count. Due to a long half-life in tissue, male study participants should use an additional barrier method of contraception for 30 days following the last dose of birinapant.

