3.1 Inclusion Criteria

- 3.1.1 Patients must have histologically or cytologically confirmed locally recurrent HNSCC, including nasopharyngeal or sinonal cancer for whom re-irradiation for local control is considered standard of care.
- 3.1.2 Patients with HPV-negative or HPV-positive head and neck cancer are eligible.
- 3.1.3 Patients who have had prior treatment with immune therapies are eligible.
- 3.1.4 Patients must have received curative-intent platinum- and/or cetuximab-based chemoradiotherapy or radiotherapy alone.
- 3.1.5 Patients must have completed their last treatment dose with chemotherapy or immunotherapy at least 4 weeks (6 weeks for nitrosoureas or mitomycin C) before enrolling on study.
- 3.1.6 Patients must have completed their last treatment dose with radiotherapy at least 6 months before enrolling on study.
- 3.1.7 Patients who have had major surgery must be fully recovered and require a recovery period of at least 4 weeks prior to enrolling on study.
- 3.1.8 Age ≥ 18 years.
- 3.1.9 ECOG performance status ≤ 2 (see [Appendix A](#)).
- 3.1.10 Patients must have normal organ and marrow function as defined below:

- Hemoglobin	≥ 9 g/dL (transfusion permitted)
- Absolute neutrophil count	$\geq 1,500/\text{mcL}$
- Platelets	$\geq 100,000/\text{mcL}$
- Total bilirubin institutional limits	within $1.5 \times$ the upper limit of normal (ULN)
- AST(SGOT)/ALT(SGPT)	$\leq 2.5 \times$ institutional upper limit of normal
- Serum creatinine	$\leq 1.5 \times$ upper limit of normal (ULN), OR :
Creatinine clearance	≥ 50 mL/min according to Cockcroft Gault formula or other institutional methods.
- Cardiac function	Patients must have a QTcF ≤ 480 msec.
- INR	INR ≤ 1.5 and no clinically significant bleeding event

within the past six months

- 3.1.11 Ability to understand and the willingness to sign a written informed consent document.
- 3.1.12 Patients must have measurable disease, per RECIST 1.1. See Section [12](#) for the evaluation of measurable disease.

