3.2 Exclusion Criteria

- 3.2.1 Eligibility for curative-intent surgery, unless the patient is considered a poor surgical candidate related to resectability, functional outcome, or prefers non-surgical therapy.
- 3.2.2 More than 2 lines of palliative systemic therapy (platinum-, taxane- or cetuximab-based chemotherapy or immunotherapy)
- 3.2.3 Patients who are receiving any other investigational agents.
- 3.2.4 Patients with known brain metastases should be excluded from this clinical trial because of their poor prognosis and because they often develop progressive neurologic dysfunction that would confound the evaluation of neurologic and other adverse events.
- 3.2.5 History of allergic reactions attributed to compounds of similar chemical or biologic composition to birinapant.
- 3.2.6 Uncontrolled intercurrent illness including, but not limited to, ongoing or active infection, symptomatic congestive heart failure, unstable angina pectoris, cardiac arrhythmia, or psychiatric illness/social situations that would limit compliance with study requirements.
- 3.2.7 Pregnancy or lactation period. Pregnant women are excluded from this study because birinapant may have potential for teratogenic or abortifacient effects. Because there is an unknown but potential risk for adverse events in nursing infants secondary to treatment of the mother with birinapant, breastfeeding should be discontinued prior to enrollment. A negative pregnancy test is required for women of childbearing potential. Women who are postmenopausal (age-related amenorrhea \geq 12 consecutive months, or who had undergone hysterectomy or bilateral oophorectomy are exempt from pregnancy testing. If necessary, to confirm postmenopausal status, a FSH level may be included at screening.
- 3.2.8 HIV positive patients on combination antiretroviral therapy are

ineligible because of the potential for pharmacokinetic interactions with birinapant.

3.2.9 Patients requiring the use of anti-tumor necrosis factor (anti TNF) therapies, such as infliximab, or patients who have received treatment with anti-TNF therapies within 5 half-lives of the drug (48 days for infliximab, 55 days for golimumab, 70 days for certolizumab and adalimumab, and 16 days for etanercept).

3.2.10 Patients with previous exposure to birinapant.

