4.3.2 OPEN/IWRS User Requirements

OPEN/IWRS users must meet the following requirements:

- Have a valid CTEP-IAM account (*i.e.*, CTEP username and password).
- To enroll patients or request slot reservations: Be on an ETCTN Corresponding or Participating Organization roster with the role of Registrar. Registrars must hold a minimum of an AP registration type.
- To approve slot reservations or access cohort management: Be identified to Theradex as the “Client Admin” for the study.
- Have regulatory approval for the conduct of the study at their site.

Prior to accessing OPEN/IWRS, site staff should verify the following:

- All eligibility criteria have been met within the protocol stated timeframes.
- If applicable, all patients have signed an appropriate consent form and HIPAA authorization form.

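### Section 8.1 bars birinapant in ongoing or recent (5-year) autoimmune disease, but no eligibility criterion in Section 3 excludes these patients

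*Combined protocol and SAP*

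**What the plan says.** The Patient Care Implications paragraph of Section 8.1 notes that birinapant synergizes with TNFα in vitro and then lists who should not be given the drug. Besides patients with a serious active infection within 2 weeks of dosing, it names those with "ongoing autoimmune disease or a recent history (within last 5 years) of autoimmune disease should not receive birinapant". It continues: "Patients receiving anti-TNF therapies should not receive birinapant", and "Birinapant should not be administered to women study participants who are pregnant or nursing". The autoimmune restriction has a defined look-back and no exemption for mild or controlled disease.

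Section 3 holds the eligibility criteria, 3.1.1 to 3.1.13 and 3.2.1 to 3.2.10. None names autoimmune disease. The nearest items are 3.2.6, "Uncontrolled intercurrent illness including, but not limited to, ongoing or active infection, symptomatic congestive heart failure", and 3.2.9, "Patients requiring the use of anti-tumor necrosis factor (anti TNF) therapies, such as infliximab", which adds washout periods by drug. Criterion 3.1.3 states: "Patients who have had prior treatment with immune therapies are eligible".

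Before registration, Section 4.3.2 asks site staff to verify this: "All eligibility criteria have been met within the protocol stated timeframes". Section 4.3.3 directs the eligibility check to Section 3.1, and Section 5.4.1 (specimen tracking) directs it to Section 3. None of the three refers to Section 8.

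**The concern.** The protocol gives two answers to one question. Section 3 decides who may enter, and Section 8.1 decides who may be dosed. For one group of patients the first says yes and the second says no. A site that applies Section 3 correctly can register a patient whom the protocol says not to treat.

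The stakes are patient safety and uniform conduct across sites. The restriction directly follows the remark about synergy with TNFα, and Section 2.4 rests the trial's rationale on radiation inducing TNFα. It also says that toxicities of the combination with radiation are unknown. Nothing in the documents gives a reason to relax the restriction in this setting. Under Section 6.1.1 as amended, up to 3 patients may now be enrolled in each of cohorts 3 and 4 (17 and 24 mg/m²) without the former observation period between patients.

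If a site does notice Section 8.1, but only after registration, a reserved slot has been used and the registration may have to be cancelled (Section 4.4). The amendment letter describes this trial as very slow to accrue.

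**Working it through.** No formula applies; the check is a comparison of text.

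**Step 1. Match each do-not-dose condition in Section 8.1 to Section 3.**

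| Condition in Section 8.1 | Counterpart in Section 3.2 | Match |
|---|---|---|
| Serious active infection, 2-week window | 3.2.6, ongoing or active infection | Yes, without the 2-week window |
| Autoimmune disease, ongoing or within 5 years | None | **No** |
| Anti-TNF therapy | 3.2.9, with washout periods | Yes |
| Pregnancy | 3.2.7, "Pregnancy or lactation period. Pregnant women are excluded from this study" | Yes |
| Nursing | 3.2.7, lactation | Yes |

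Matched: 4 of 5. Unmatched: 5 − 4 = 1. The contraception requirement in the same part of Section 8.1 is also carried into Section 3, as 3.1.13.

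**Step 2. Count the criteria.** 13 inclusion + 10 exclusion = 23, of which 0 name autoimmune disease. The numbering is unbroken in both lists, so no criterion is missing from the text.

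**Step 3. See how far the nearest criteria reach.**

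- 3.2.6 is open-ended but confined to uncontrolled illness. It can take in active, uncontrolled autoimmune disease. It does not reach controlled disease and has no look-back.
- 3.2.9 takes in patients who need anti-TNF drugs or received them within the washout. It does not reach patients managed in other ways or on no treatment.
- Left over are patients with controlled autoimmune disease not on anti-TNF drugs, and patients whose disease resolved within the last 5 years. Section 8.1 bars both groups; Section 3 admits both.

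**Step 4. See whether registration would stop them.** Section 4.3.2 speaks of all eligibility criteria without naming a section, 4.3.3 cites Section 3.1, and 5.4.1 cites Section 3. Under any of these the patient passes, because the restriction sits only in Section 8.1. The Study Calendar (Section 11) has medical history taken at screening, so the condition may be recorded, but no eligibility item tells staff to act on it.

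**The case against.** The strongest reply is that the rule is already in force. Section 8.1 is part of the same protocol, and nothing in Section 3 says these patients may be dosed, so a reader who follows both sections does not treat them. A mistaken registration can be cancelled under Section 4.4. Part of the group is already excluded by 3.2.6 and 3.2.9. The size of the remainder is unknown, and the documents report no harm in it. The count of five conditions also depends on how they are split; treating pregnancy and nursing as one would make it 1 of 4.

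Most of this stands, and it limits the point. The defect is one of placement, not a missing prohibition, and no harm can be quantified. The count only summarises the comparison: however the conditions are grouped, autoimmune disease is the one without a counterpart.

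The reply does not remove the conflict. Entry is decided on Section 3, and the safeguard for this group depends on someone recalling a paragraph in the pharmaceutical section. The authors made the neighbouring anti-TNF restriction an eligibility criterion with detailed washouts, and no text explains why the autoimmune restriction was handled differently.

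It is also fair to say that Section 4.3.3 cites only the inclusion list, so read literally it would not check a new line in 3.2. That is a reason to correct the cross-reference as well.

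**Conclusion.** The inconsistency is real and should be fixed. One of the five conditions under which Section 8.1 says birinapant should not be given has no counterpart among the 23 eligibility criteria. Followed as written, Section 3 admits patients with controlled autoimmune disease not on anti-TNF drugs, and patients with disease resolved within 5 years.

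The conclusion rests on reading 3.2.6 as limited to uncontrolled illness, which is what it says. It does not depend on any prevalence figure. The documents give none for autoimmune disease in this population, so neither the number of patients nor the risk can be stated. A patient would be dosed against Section 8.1 only if that section were overlooked, and the documents do not show that this has happened. No effect on the MTD, power or sample size follows.

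The consent pages and part of the appendices were not in the text available for review. Whether they repeat the restriction could not be checked, but repeating it there would not make it an eligibility criterion.

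**What to change.** Add an exclusion to Section 3.2 covering ongoing autoimmune disease and any autoimmune disease in the past 5 years, so that it agrees with Section 8.1. If minor or controlled conditions are meant to be allowed, write the exemption in both sections. If leaving the item out of Section 3 was intended, revise Section 8.1 instead and give the reason.

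Three smaller items belong in the same amendment:

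- Make the eligibility reference in Section 4.3.3 point to all of Section 3.
- Say whether immune-related events after earlier immunotherapy count as autoimmune disease, since 3.1.3 admits patients with prior immune therapy and Section 8.1 is silent on this.
- As a precaution, check the screening histories of enrolled patients, and of the 2 participants awaiting enrollment at the time of the amendment. Nothing in the documents suggests that any of them is affected.

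The cost is one line of text and no new procedure, because medical history is already collected at screening. The eligible pool narrows only by patients whom Section 8.1 already says not to treat. It would narrow further, by an amount the documents do not give, if the sponsor decides that immune-related events count.

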8.1.1 Availability

Birinapant is an investigational agent supplied to investigators by the Division of Cancer Treatment and Diagnosis (DCTD), NCI.

Birinapant is provided to the NCI under a Collaborative Agreement between the Pharmaceutical Collaborator and the DCTD, NCI (see Section [13.3](#)).

8.1.2 Agent Ordering and Agent Accountability

8.1.2.1 NCI-supplied agents may be requested by eligible participating Investigators (or their authorized designee) at each participating institution. The CTEP-assigned protocol number must be used for ordering all CTEP-supplied investigational agents. The eligible participating investigators at each participating institution must be registered with CTEP, DCTD through an annual submission of FDA Form 1572 (Statement of Investigator), NCI Biosketch, Agent Shipment Form, and Financial Disclosure Form (FDF). If there are several participating investigators at one institution, CTEP-supplied investigational agents for the study should be ordered under the name of one lead participating investigator at that institution.

8.1.2.2 Birinapant clinical supplies may be ordered when a patient is in screening.

8.1.2.3 Submit agent requests through the PMB Online Agent Order Processing (OAOP) application. Access to OAOP requires the establishment of a CTEP Identity and Access Management (IAM) account and the maintenance of an “active” account status, a “current” password, and active person registration status. For questions about drug orders, transfers, returns, or accountability, call or email PMB any time. Refer to the PMB’s website for specific policies and guidelines related to agent management.

8.1.2.4 Agent Inventory Records – The investigator, or a responsible party designated by the investigator, must maintain a careful record of the receipt, dispensing and final disposition of all agents received from the PMB using the appropriate NCI Investigational Agent (Drug) Accountability Record (DARF) available on the CTEP forms page. Store and maintain separate NCI Investigational Agent Accountability Records for each agent, strength, formulation and ordering investigator on this protocol.

8.1.3 Investigator Brochure Availability

The current versions of the IBs for the agents will be accessible to site investigators and research staff through the PMB OAOP application. Access to OAOP requires the establishment of a CTEP IAM account and the maintenance of an “active” account status and a “current” password. Questions about IB access may be directed to the PMB IB Coordinator via email.

9 STATISTICAL CONSIDERATIONS

9.1 Study Design/Endpoints

The primary objective is to determine the toxicities and MTD of birinapant administered concurrently with IMRRT.

The secondary objectives are to determine the response rate, local-regional control, PFS and OS; to determine if FADD and/or BIRC2/3 copy gain in tumor tissue are associated with improved response, locoregional control, progression-free survival and overall survival; and to determine the feasibility of detecting effects of birinapant and re-irradiation on pilot pharmacodynamic markers in tumor tissue, including microwestern for decrease in drug targets IAP1/2; increase in apoptosis/necroptosis markers Caspase 3 and MLKL.

9.2 Sample Size/ Accrual Rate

This trial will initially consist of a 4 dose levels 3+3 escalation phase; with up to 6 patients per dose level, up to 24 patients may be required to determine the MTD. Then, at the MTD, an additional 10 patients will be treated in order to determine more precise estimates of safety and toxicity of patients as well as to address secondary objectives. If there are 16 patients at the MTD including the expansion cohort, then there would be approximately 80% power to detect an effect size of 2.0 for a given test comparing two groups or comparing pre-treatment values to on-treatment values with a 1.0 effect size, with a 0.01 two-tailed significance test. This would be sufficient to allow for up to 6 tests to be performed while holding the overall significance level to 0.05, taking into consideration enough patients to allow for a Bonferroni correction. In practice, given the exploratory nature of the marker and related analyses, the results may be presented without any such formal correction, but in the context of the number of such tests performed. As an illustration, if IAP1, CASP3, and MLKL were each obtained pre-treatment and at day 4 on treatment, with 16 total patients at the MTD, there would be adequate patients so that the

differences could each be tested with at least 80% power with an effect size equal to 1.0 times the standard deviation of the difference, with a 0.01 two-tailed significance test. In addition, although with less power depending on the fraction of patients who respond, comparisons could be made of the changes in these parameters between patients who respond or do not respond.

If all dose levels are evaluated and 10 additional patients are included at the MTD, we anticipate enrolling a minimum of 16 patients and a maximum of 34 patients. It is anticipated that 1-2 patients/month may be enrolled onto this trial.

Primary endpoints will be the DLTs and other toxicities, and the MTD for the regimen.

For DLT and MTD determination, escalation will proceed with the 3+3 dose escalation design until either the stopping rule below or the MTD is reached.

No. of patients with DLT's at this dose level	No. of patients treated at this dose level	Action
Dose escalation rules		
0	3	Treat 3 patients at the next higher dose level (or add 3 patients if at the highest level).
1	3	Treat 3 additional patients at this dose level.
1	6	Treat 3 patients at the next higher dose level (or if at the highest level, declare the dose at this level to be the MTD).
>1	3 or 6	Stop dose escalation; begin dose de-escalation. De-escalate one dose level.

The DLT evaluation period between dose levels will be 42 days during drug/radiation treatment plus 14 (+/- 3) days of follow-up thereafter. Patients are considered evaluable for toxicity if they have received at least 1 dose of birinapant. Patients that are not evaluable will be replaced. A standard “3+3” design, described in the table below, will be followed.

PLANNED ENROLLMENT REPORT

Racial Categories	Ethnic Categories					Total
	Not Hispanic or Latino		Hispanic or Latino			
	Female	Male	Female	Male		
American Indian/ Alaska Native	0	0	0	0		0
Asian	0	2	0	0		2
Native Hawaiian or Other Pacific Islander	0	0	0	0		0
Black or African American	1	3	0	2		6
White	5	19	0	1		25
More Than One Race	0	1	0	0		1
Total	6	25	0	3		34

PHS 398 / PHS 2590 (Rev. 08/12 Approved Through 8/31/2015)

OMB No. 0925-0001/0002

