Date: December 15, 2022
 From: [name], TGMB, NCI
 To: CTEP, NCI
 Subject: Response to Amendment to CTEP for protocol 19C0041_10184 entitled, Birinapant and Intensity Modulated Re-Irradiation Therapy (IMRRT) for Locoregionally Recurrent Head and Neck Squamous Cell Carcinoma (HNSCC)

We respectfully submit an amendment to protocol #10184 (**version date 12/15/2022**) to CTEP for **urgent** review. The main purpose of this amendment is to allow 3 participants at a time to be enrolled in each dose cohort. The protocol currently allows just one participant to be enrolled at a time. There are currently 2 eligible participants awaiting enrollment at 2 participating sites. This study has been very slow to accrue and this change will allow both participants to enroll soon for treatment and concurrently. The risk profile of the study so far has been very safe, with no DLTs that mandated enrollment of 3 more participants in each of the first two dose cohorts. Furthermore, the safety of birinapant as monotherapy at much higher doses ($47\text{mg}/\text{m}^2$) has already been established in other phase I studies (<https://pubmed.ncbi.nlm.nih.gov/26333381>).

This amendment has been discussed with [name] who agrees this may be submitted as an urgent amendment for expedited review.

Thank you for your consideration of this amendment. The changes are detailed below.

SUMMARY OF CHANGES – Protocol

#	Section	Change
1.	Header	The version date was updated in the header throughout.
2.	Title Page	
 [name] has been removed as a co-investigator. He has left the NIH. Study coordinator and contact info has been updated. The protocol version number and date were updated.
3.	Section 6.1.1 , Dose Escalation Cohort	Language has been added in order to allow up to 3 patients to be enrolled in each remaining cohort for the remainder of the trial. The protocol currently allows just one participant to be enrolled at a time. There are currently 2 eligible participants awaiting enrollment at 2 participating sites. This study has been very slow to accrue and this change will allow both participants to enroll soon for treatment and concurrently. The risk profile of the study so far has been

NATIONAL CANCER INSTITUTE
Center for Cancer Research

#	Section	Change

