Dose levels are defined in the table below. Starting dose will be 5.6 mg/m². If >1/6 patients develop a DLT at level 1 dose and a maximum 1/6 patients develop a DLT at the level -1 dose, the latter will be determined as the MTD.

Table 1: Dose Escalation Schedule

Dose Level	Birinapant (mg/m ²)
Level -1	2.8
Level 1	5.6
Level 2	11
Level 3	17
Level 4	24

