≥ 2	Dose escalation will be stopped. This dose level will be declared the maximally administered dose (highest dose administered). Three (3) additional patients will be entered at the next lowest dose level if only 3 patients were treated previously at that dose.
1 out of 3	Enter at least 3 more patients at this dose level. 
• If 0 of these 3 patients experience DLT, proceed to

	
the next dose level.
 
• If 1 or more of this group suffer DLT, then dose escalation is stopped, and this dose is declared the maximally administered dose. Three (3) additional patients will be entered at the next lowest dose level if only 3 patients were treated previously at that dose.
≤1 out of 6 at highest dose level below the maximally administered dose	This is generally the MTD. At least 6 patients must be entered at the MTD.

This dose escalation plan, on average, will select a maximum tolerated dose with the specified acceptable probabilities of DLT.

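### Section 9.2 gives a minimum of 16 patients if all dose levels are evaluated, but the 3+3 rules in 9.2 and 6.2 need 25; it also fits six tests at 0.01 within an overall 0.05, when they sum to 0.06

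*Combined protocol and SAP*

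**What the plan says.** Section 9.2 describes the design in these words: "This trial will initially consist of a 4 dose levels 3+3 escalation phase". With up to 6 patients per level, it says "up to 24 patients may be required to determine the MTD", and 10 more are then treated at the MTD. The enrolment range follows: "If all dose levels are evaluated and 10 additional patients are included at the MTD, we anticipate enrolling a minimum of 16 patients", with a maximum of 34. Expected accrual is 1-2 patients per month.

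The counting rules are these:

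- **Section 9.2 table.** 0 DLTs in 3 means 3 patients at the next level, or 3 more if already at the highest level. 1 in 3 means 3 more at the same level. 1 in 6 means escalate, or declare the MTD at the highest level. More than 1 in 3 or 6 means de-escalate.
- **Section 6.2.** "At least 6 patients must be entered at the MTD". The level below a too-toxic level receives 3 more patients if only 3 were treated there.
- **Section 6.1.1.** If level 1 is too toxic and "a maximum 1/6 patients develop a DLT at the level -1 dose, the latter will be determined as the MTD".
- **Section 9.2, on evaluability.** "Patients that are not evaluable will be replaced".

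On multiplicity, section 9.2 says that 16 patients at the MTD give about 80% power with a 0.01 two-tailed test, for an effect size of 2.0 between two groups or 1.0 for paired differences. It continues: "This would be sufficient to allow for up to 6 tests to be performed while holding the overall significance level to 0.05", with reference to a Bonferroni correction. The next sentence allows results to be presented without formal correction.

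**The concern.** The minimum carries its own condition, that every dose level has been evaluated. Sixteen patients cannot fill four levels and a 10-patient expansion: after the expansion only 6 remain for four levels that each need at least 3. The same section uses 16 for the number at the MTD including the expansion, so a subgroup count seems to have been reused as the trial total.

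The minimum is the lower end of the accrual forecast and stands beside the monthly accrual rate. A reader planning accrual, drug supply or study duration from it starts from a number the design cannot produce. The maximum has a gap of scope: it counts levels 1 to 4 only, although level -1 can become the MTD.

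The alpha sentence ties six tests to a per-test level that Bonferroni assigns to five.

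**Working it through.** **Inputs.** Four levels, up to 6 patients each, expansion of 10, and the escalation table (section 9.2). At least 6 at the MTD, and the refill of the level below a toxic one (section 6.2). Level -1 as a possible MTD (section 6.1.1). Per-test alpha 0.01 two-tailed, six tests, overall 0.05, 16 patients, effect sizes 1.0 (paired) and 2.0 (two groups) (section 9.2).

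**Figures that reproduce.**

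- Escalation maximum: 4 x 6 = 24. Total maximum: 24 + 10 = 34.
- Number at the MTD: 6 + 10 = 16.
- Paired power at 0.01, n = 16, effect 1.0 (noncentral t, 15 df, noncentrality 1.0 x sqrt(16) = 4): 83.5%, which agrees with the stated at least 80%.
- Two-group power at 0.01, effect 2.0, 8 v 8 split (14 df, noncentrality 2.0 / sqrt(1/8 + 1/8) = 4): 82.6%, against about 80% stated. The equal split is an assumption.

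**Minimum enrolment.** All 3+3 paths were enumerated with full cohorts and 6 required at the MTD. Then 10 were added to each path that ends in an MTD.

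| Path | Count | Total |
|---|---|---|
| All four levels, MTD = level 4 | 3 + 3 + 3 + 6 + 10 | 25 |
| All four levels, level 4 too toxic in its first 3, MTD = level 3 | 3 + 3 + 6 + 3 + 10 | 25 |
| Shortest route, MTD = level 1 | 6 + 3 (level 2) + 10 | 19 |
| Shortest route, MTD = level -1 | 3 (level 1) + 6 (level -1) + 10 | 19 |

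No path that ends in an MTD with expansion gives 16. That total would need level 1 declared the MTD with level 2 untested, whereas the table sends 0/3 or 1/6 at level 1 up to level 2. The row in section 6.2 for 2 or more DLTs gives no denominator. If a cohort may close after 2 DLTs in 2 patients, the minima become 24 (3 + 3 + 6 + 2 + 10) and 18 (6 + 2 + 10).

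The amendment cover letter reports "no DLTs that mandated enrollment of 3 more participants in each of the first two dose cohorts". If this means that levels 1 and 2 each closed at 0/3, which is an inference, the smallest full-cohort total still possible is 3 + 6 + 3 + 10 = 22: level 3 is too toxic and level 2 is refilled.

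**Maximum with level -1.** Levels 1 to 3 each clear at 0/3, level 4 fails at 6, and levels 3, 2 and 1 each fail on refill to 6. Level -1 then takes 6. Escalation: 5 x 6 = 30. Total: 30 + 10 = 40. Replacements would be added to any of these totals.

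**Accrual time at 1-2 patients per month, ignoring DLT waiting time.** 16 patients: 16/2 to 16/1 = 8 to 16 months. 25 patients: 25/2 to 25/1 = 12.5 to 25 months.

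**Alpha.**

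- Bonferroni sum for six tests: 6 x 0.01 = 0.06. If independent: 1 - 0.99^6 = 0.0585.
- Five tests: 5 x 0.01 = 0.05.
- Level for six tests: 0.05/6 = 0.0083.

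**Power with 16 patients at 0.0083.** Paired, effect 1.0: 81.3%. Two groups, effect 2.0: 80.4% at 8 v 8, 77.2% at 6 v 10 and 65.3% at 4 v 12. The plan states no split.

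**The case against.** **Alpha.** The sentence can be read as saying only that 16 patients are enough for six corrected tests. On that reading it is nearly right: power at 0.0083 is 81.3% paired and 80.4% for equal groups, and 0.0083 rounds to 0.01. The marker tests are secondary or exploratory, and formal correction may be omitted. All of this limits the consequence. It does not make 0.01 the Bonferroni level for six tests, and the sentence follows directly from a 0.01 test.

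**Level -1.** Section 9.2 speaks of four dose levels, so 24 and 34 are correct for what they describe, and quoting evaluable patients before replacements is common. Reaching 40 needs an improbable sequence: with independent patients and the DLT rate at each level chosen to favour it, its probability stays below 0.02%. This stands. The maximum needs a statement of scope; it is not a miscalculation.

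**Where 25 comes from.** The 9.2 table alone does not force 6 patients at level 3 when level 4 is too toxic; that comes from section 6.2. Without it, that path would total 22. The point is fair, but section 6.2 is part of the same plan, and 22 is still not 16.

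**Other limits.** A trial that finds levels 1 and -1 both too toxic can stop at 6 patients, so the claim that 16 is unreachable applies only to paths with an MTD and expansion. Those are the paths the sentence in 9.2 describes. The month figures leave out the evaluation period between levels (42 days plus 14), and the cover letter calls accrual very slow, so they serve only to compare 16 with 25. No rule depends on the minimum, and the planned enrolment table already uses 34.

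**Conclusion.** Both figures are wrong as written, and the point is minor.

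The minimum should be 25 on its stated condition, so it is understated by 9 patients. This rests on full cohorts, 6 patients at the MTD, an expansion of 10 and no replacements; early closure of a cohort at its second DLT would lower it only to 24. Dropping the all-levels condition gives 19 (18 with early closure), still above 16.

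The maxima are correct for levels 1 to 4 and incomplete for the design as a whole.

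Six tests at 0.01 have a Bonferroni bound of 0.06. Correcting the level costs 2.2 points of paired power (83.5% - 81.3%). Two-group power stays at about 80% only if the groups are close to equal.

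**What to change.** In section 9.2:

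1. Replace 16 with 25 as the minimum when all four levels are evaluated, and give 19 as the smallest total from the start of the trial for an MTD plus expansion. If levels 1 and 2 did close at 0/3, the sponsor could add that the smallest total still possible is 22.
2. Say that 24 and 34 count levels 1 to 4 only, that use of level -1 could take them to 30 and 40, and that replacements come on top.
3. Either keep 0.01 and say five tests, or keep six tests and state 0.0083. With 0.0083, quote 81.3% paired power, and give two-group power with the split it assumes.

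As an option, show paired power at 0.01 by number of complete pairs. The stated at least 80% is correct for 16 pairs, but the frozen biopsies are optional (section 5.1).

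| Complete pairs | 16 | 15 | 14 | 12 | 10 | 8 |
|---|---|---|---|---|---|---|
| Power | 83.5% | 79.7% | 75.2% | 64.2% | 50.4% | 34.8% |

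The cost is wording only: no added patients and no change to any escalation rule. If the sponsor wants the enrolment ceiling to cover level -1, the planned enrolment table (34) must change as well.
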